8.9	Safety committee	20
8.10	Reporting of results.....	20
8.11	Conflict of interest and financial support.....	20
9	Reference list.....	21

Page

List of abbreviations

ADE:	Adverse device effect
AE:	Adverse event
BG:	Blood glucose
°C:	Centigrade
CA:	Competent authority
CIP:	Clinical investigation plan
CGM:	Continuous glucose monitoring
CRA:	Clinical research associate
CRF:	Case report form
CRO:	Contract research organisation
EC:	Ethics committee
ECG:	Electrocardiogram
EEG:	Electroencephalogram
FAS:	Full analysis set
HV:	Healthy volunteers
ISO:	International standard organisation
MedDRA:	Medical dictionary for regulatory activities
PG:	Plasma glucose
PP:	Per protocol
SADE:	Serious adverse device effect
SAE:	Serious adverse event
SOC:	Standard operation classification
TEAE:	Treatment emergent adverse events
V:	Voltage

1 Background information and justification for conducting the study

1.1 Background

1.1.1 Hypoglycaemia in patients with type 1 diabetes

The near-normalisation of glucose levels has become an established goal in diabetes treatment in order to reduce the risk of late complications such as nephropathy, neuropathy, retinopathy and cardiovascular disease (1). The fear of hypoglycaemia, the most common adverse event (AE) associated with insulin treatment in patients with diabetes (2), discourages patients from maintaining tight glycaemic control and only a minority of the patients reach the defined goal of glucose control, leading to increased diabetes related morbidity and mortality (3–7). Symptoms of hypoglycaemia can be classified as autonomic (warning) symptoms caused by the release of catecholamines, or neuroglycopenic symptoms caused by the lack of glucose supply to the brain. Following long-term diabetes duration and tight glycaemic control, autonomic symptoms may be

compromised due to impaired glucose counter regulatory response. Between 1/4 and 1/3 of patients with type 1 diabetes suffer from impaired awareness or unawareness to hypoglycaemia (5,8,9).

1.1.2 A hypoglycaemia alarm based on electroencephalography

The electroencephalogram (EEG) reflects the functional state and metabolism of the brain. The brain is critically dependent on a continuous supply of glucose, and when the glucose level is lower than the metabolic requirements of the brain, brain function deteriorates. Neuroglycopenic hypoglycaemia in insulin-treated patients with diabetes is associated with characteristic changes in EEG, including a decrease in alpha activity and an increase in delta and theta activity (10–13). These changes are clearly seen at blood glucose level of ~2.0 mmol/L (10,11) preceding the development of severe cognitive dysfunction (14).

Sleep EEG differs significantly from daytime EEG with periods of deep sleep defined by the presence of slow wave dominance. Approximately 50% of all hypoglycaemic episodes occur during sleep, and prolonged episodes of hypoglycaemia as measured by continuous glucose monitoring (CGM) occur in 8.5% of all nights in both children and adults (15).

For the device to have clinical applicability, it should be able to distinguish hypoglycaemia-induced EEG changes from noise, artefacts and physiological variations in the EEG including the low-frequency waves seen during sleep, with high sensitivity and specificity using an algorithm that classifies the EEG in real-time. There should be a timely difference between hypoglycaemia-induced EEG changes and severe cognitive impairment. The device must be fully compatible with everyday activities. Thus, the device should be small, biocompatible and implantable, and the monitoring and processing unit should be small and have sufficient battery power.

1.2 Rationale for study

While a finger prick test accurately measures the blood glucose level, it does not provide continuous measurements, and hence it is unreliable as a hypoglycaemia alarm. Recent studies have indicated that the use of CGM reduces the risk of severe hypoglycaemia (19). However, some find these devices troublesome to use and are annoyed by the inaccuracy of the measurements, and even after short term use the coverage in subgroups of patients is as low as 50% of the time (20–22). Thus there is a medical need for a reliable hypoglycaemia alarm which is easy and convenient to use and with high sensitivity and high rate of positive prediction.

The current protocol describes a clinical study designed to evaluate the sensitivity and the positive predictive value of the hyposafe H02 in subjects with type 1 diabetes during everyday activities and during insulin-induced hypoglycaemia. In addition, information regarding safety and usability will be collected and analysed. This is to verify that the hyposafe H02 is working as intended in subjects with type 1 diabetes before proceeding with the planned larger study in subjects with type 1 diabetes.

2 Study objectives and endpoints

2.1 Objectives

2.1.1 Primary objectives

Performance

To evaluate the technical performance of the hyposafe H02 during everyday activities and during insulin-induced hypoglycaemia in subjects with type 1 diabetes.

Safety

To evaluate potential safety issues associated with the implantation and use of the hyposafe H02 in subjects with type 1 diabetes.

2.1.2 Secondary objective

Usability

To evaluate the usability of the hyposafe H02 during everyday activities in subjects with type 1 diabetes.

2.2 Endpoints

Primary performance endpoints

- Sensitivity: Proportion of spontaneous hypoglycaemic episodes detected by the hyposafe H02 compared to the total number of validated¹ spontaneous hypoglycaemic episodes after 12 weeks of monitoring (from visit 5 to visit 10)
- Positive predictive value: Proportion of validated¹ spontaneous hypoglycaemic episodes detected by the hyposafe H02 compared to the total number of alerts from the hyposafe H02 after 12 weeks of monitoring (from visit 5 to visit 10)

Secondary performance endpoints

- Overall sensitivity: Overall proportion of hypoglycaemic episodes detected by the hyposafe H02 compared to the total number of validated² hypoglycaemic episodes after 12 weeks of monitoring (from visit 5 to visit 10)
- Overall positive predictive value: Overall proportion of validated² hypoglycaemic episodes detected by the hyposafe H02 compared to the total number of alerts from the hyposafe H02 after 12 weeks of monitoring (from visit 5 to visit 10)
- Sensitivity: Proportion of insulin-induced hypoglycaemic episodes detected by the hyposafe H02 compared to the total number of insulin-induced hypoglycaemic episodes

¹ Validated by self-measured blood glucose (SMBG) or clinical hypoglycaemia according to subject's experience

² Validated by self-measured blood glucose (SMBG), plasma glucose (PG) or clinical hypoglycaemia according to subject's experience

- Positive predictive value: Proportion of insulin-induced hypoglycaemic episodes detected by the hyposafe H02 compared to the total number of alerts from the hyposafe H02
- Number of participants with a satisfactory EEG Quality test
- Change in impedance (from visit 5 to visit 10)
- Number of device complaints (from visit 4 to visit 10)
- Mean glucose level at the time of a hypoglycaemia alarm

Primary safety endpoint

- Number of AEs 17 weeks after implantation (from visit 3 to visit 12)

Secondary safety endpoint

- Number of adverse device effects (ADEs) 17 weeks after implantation (from visit 3 to visit 12)

Secondary usability endpoints

- Development in discomfort over time (visit 5 to visit 10)
- User satisfaction (visit 8)
- Mean number of hours of use per hyposafe H02 device (from visit 4 to visit 10)
- Response to hypoglycaemia alarm (from visit 5 to visit 10)
- Assessment of alarm fatigue (visit 12)

3 Study design - overview

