3.1 Description of study design

The present study is a 4-month non-controlled observational study in subjects with type 1 diabetes. Subjects will attend a screening visit (visit 1) in order to assess their eligibility, followed by an inclusion visit (visit 2) which should take place as soon as all screening results (including laboratory results) are available, reviewed and the subject is confirmed eligible. 12-20 subjects are planned to be enrolled, and withdrawals will be replaced until at least 12 subjects have completed the study.

The subjects will have the implantable part of the hyposafe H02 device implanted (see Figure 1). Subjects will be exposed to insulin-induced hypoglycaemia twice during the study. A device for continuous glucose monitoring (CGM) will be mounted for two periods of approximately 5 days. They will wear the hyposafe H02 device as much as possible both during daytime and night-time. In addition, they will fill out questionnaires and complete an interview regarding use, discomfort and satisfaction related to the implantation and the use of the H02 device.

Subjects will have the implantable part of the hyposafe H02 device implanted at visit 3 by a surgical procedure under local anaesthesia. External parts of the hyposafe H02 device will be mounted at visit 4 and fitted if needed at each subsequent visit until visit 10 (see flow chart Table 1).

The duration of the study from screening (visit 1) to removal of sutures (visit 12) will be approximately 18 weeks.

This study will be conducted in accordance with this investigational plan, ISO 14155:2011, ethics committee requirements, the Declaration of Helsinki (23), applicable local governmental regulations, and appropriate regulations for clinical studies.

4 Study population

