7.5 Endpoint analysis

7.5.1 Performance endpoints

All performance endpoints will be analysed using the FAS as well as the PP analysis set.

Primary performance endpoint

The primary performance endpoints are defined as the sensitivity and positive predictive value of the hyposafe H02 based on spontaneous hypoglycaemic episodes.

Spontaneous hypoglycaemic episodes are recorded by subjects in the log book throughout the study. This includes information on blood glucose measurements before treating the episode, alarms given by the hyposafe H02 device and information on whether the subjects was able to treat him/herself or was asleep when the episode occurred.

A hypoglycaemic episode will be characterised as treatment emergent if the onset of the episode is on or after the first day the hyposafe H02 device switched to “*alarm on*”-mode and no later than the last day of the wearing the external device. Data on treatment emergent hypoglycaemic episodes are presented in terms of the number of subjects with at least one episode (N) and the number of episodes (E).

Hypoglycaemic episodes will be defined as nocturnal (i.e. during night-time) if they occur during sleep (as reported by the subject) and/or are registered by the hyposafe H02 night device.

Data from blood glucose measurement and clinical hypoglycaemia (according to subject’s experience) will be used by UNEEG™ medical to classify a hypoglycaemic alarm according to categorisation displayed in Table 2 (true and false, positive and negative hypoglycaemia alarms). As blood glucose values are lower than plasma values, a constant factor of 1.11 is used to convert concentration in whole blood to the equivalent concentration in plasma (25).

Sensitivity and positive predictive value will be calculated for daytime and night-time, separately.

Secondary performance endpoints

Insulin-induced hypoglycaemia is performed twice for each subject, with frequent assessments of plasma glucose levels. As the number of spontaneous hypoglycaemic episodes reported during the study may be relatively small, data from the insulin-induced hypoglycaemia will be added to calculate the overall **sensitivity and positive predictive value** of the hyposafe H02 (spontaneous and insulin-induced hypoglycaemia episodes) after 12 weeks of monitoring (from visit 5 to visit 10).

The sensitivity and positive predictive value will also be calculated based data from the insulin-induced hypoglycaemic episodes only.

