The hypoglycaemic alarms will be classified according to categorisation displayed in Table 2 (true and false, positive and negative hypoglycaemia alarms), and presented as described for primary performance endpoint.

Table 2 Categorisation of hypoglycaemic episodes

Episodes categorised as			
PG > 3.9mmol/l	+ alarm	+/- clinical hypoglycaemia ^{a)}	False positive 
	- alarm	+/- clinical hypoglycaemia ^{a)}	True negative 
PG 2.0 – 3.9mmol/l	+ alarm	+/- clinical hypoglycaemia ^{a)}	True positive 
	- alarm	+ clinical hypoglycaemia ^{a)}	False negative 
		- clinical hypoglycaemia ^{a)}	True negative 
PG < 2.0mmol/l	+ alarm	+/- clinical hypoglycaemia ^{a)}	True positive 
	- alarm	+/- clinical hypoglycaemia ^{a)}	False negative 
PG not measured	+ alarm	+ clinical hypoglycaemia ^{a)}	True positive 
		- clinical hypoglycaemia ^{a)}	Not categorised 
	- alarm	+ clinical hypoglycaemia ^{a)}	Not categorised  False negative ^{b)} 

^{a)} According to subject (No strict definition is given)

^{b)} If hypoglycaemic episode was severe (i.e. requiring assistance from third person whether being help for carbohydrate ingestion, glucagon injection or contact to health care person), the episodes should be characterised as false negative

PG; plasma glucose

Data from **EEG quality test** at the visit 4 and visit 10 will be compared graphically.

The **impedance** is expected to be below 5 kOhm at all times. No trend in the measurements for each subject should be apparent over time, except perhaps a small decline in the beginning. Any change in impedance over time (from visit 5 to visit 10) will be summarised descriptively and presented by subject.

The **number of device complaints** will be tabulated and presented by device part.

Mean blood, plasma or interstitial **glucose level at the time of an alarm** will be summarised for insulin-induced hypoglycaemia and spontaneous hypoglycaemic episodes, separately.

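### Primary sensitivity counts episodes that occur while the external unit is off, so it mixes detection with wear

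*Combined protocol and SAP*

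**What the plan says.** Section 2.2 gives primary sensitivity as "Proportion of spontaneous hypoglycaemic episodes detected by the hyposafe H02 compared to the total number of" validated spontaneous episodes over the 12 weeks from visit 5 to visit 10. Validation is by self-measured glucose or the subject's own experience, and neither needs the device to be on.

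Section 7.5.1 calls an episode treatment emergent if it starts on or after the first alarm-on day and "no later than the last day of the wearing the external device". The log-book items it names are glucose before treatment, alarms given, and "information on whether the subjects was able to treat him/herself or was asleep when the episode occurred". Whether the unit was on is not among them.

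Table 2 sorts episodes by plasma glucose band, alarm or no alarm, and clinical hypoglycaemia. Its footnote b adds that, where glucose was not measured, no alarm was given and the episode was severe, "the episodes should be characterised as false negative".

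On wear, section 3.1 says: "They will wear the hyposafe H02 device as much as possible both during daytime and night-time". The primary performance objective in section 2.1.1 is "To evaluate the technical performance of the hyposafe H02 during everyday activities" and during induced hypoglycaemia. Section 2.1.2 has a separate secondary objective, "To evaluate the usability of the hyposafe H02 during everyday activities in subjects with type 1 diabetes", and section 2.2 lists "Mean number of hours of use per hyposafe H02 device" among the usability endpoints.

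**The concern.** The external unit receives the implant's signal and charges it (section 5), and the implant is powered from outside through an inductive link (section 8.1). With the unit off, no alarm is possible. An episode in a break in wear is therefore a no-alarm episode whatever the quality of the algorithm, and no stated rule takes it out of primary sensitivity.

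The results are meant to inform optimisation of the algorithm (section 7.1) and to verify the device before a larger study (section 1.2). A low spontaneous sensitivity could mean that the algorithm missed episodes or that the unit was off. These call for different responses, and the single figure cannot tell them apart. The day and night sensitivities could differ only because wear differs. The overall sensitivity, which pools spontaneous with insulin-induced episodes, inherits the problem.

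Positive predictive value is not diluted directly, since an unworn unit gives no alarm. It could still shift if wear is related to when episodes occur.

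**Working it through.** **Is there a rule that removes off-device episodes?**

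- Section 2.2: the denominator has no condition on wear.
- Section 7.5.1, treatment-emergent rule: removes days before alarm-on and after the last day of wear, not the gaps between. The rule is tied explicitly to the counts of subjects and episodes. If it does not govern sensitivity, there is even less restriction.
- Section 7.2: the full analysis and per-protocol sets select subjects, not episodes.
- Section 7.4: covers withdrawals only.
- Section 7.5.3: connected hours are summarised as usability and not linked to episodes.

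No rule does.

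**How Table 2 scores a low-glucose or unmeasured episode with the unit off**

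| Plasma glucose | Clinical picture | Category |
|---|---|---|
| < 2.0 mmol/l | any | False negative |
| 2.0–3.9 mmol/l | symptoms | False negative |
| 2.0–3.9 mmol/l | no symptoms | True negative |
| Not measured | severe | False negative |
| Not measured | symptomatic, not severe | Not categorised |

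**Size**

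The plan states no expected sensitivity or wear, so there is no figure to reproduce. Let w be the share of validated episodes that start with the unit worn, s the sensitivity while worn, and f the share of no-alarm validated episodes scored false negative. Wear is taken as independent of detectability, and every alarmed episode as a true positive. Then

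reported sensitivity = w·s / [w·s + f·(1 − w·s)].

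All values of w, s and f are assumptions. The 50% lower end for w is borrowed from the continuous glucose monitoring coverage in section 1.2 and is not an H02 figure.

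*Section 2.2 wording (f = 1, so reported = w·s):*

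| s | w = 1 | w = 0.9 | w = 0.8 | w = 0.5 |
|---|---|---|---|---|
| 0.6 | 60% | 54% | 48% | 30% |
| 0.8 | 80% | 72% | 64% | 40% |
| 0.9 | 90% | 81% | 72% | 45% |

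Two different devices can give the same figure: 0.9 × 0.8 = 0.8 × 0.9 = 0.72.

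Per 100 episodes with s = 0.8 and w = 0.9, 72 are detected, 18 are missed while worn and 10 occur off the device. Wear gaps are then 10/28 = 36% of the no-alarm episodes.

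*Table 2 with half of no-alarm episodes scored false negative (f = 0.5), s = 0.8:*

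- w = 1: 0.80 / (0.80 + 0.5 × 0.20) = 88.9%
- w = 0.9: 0.72 / (0.72 + 0.5 × 0.28) = 83.7%
- w = 0.5: 0.40 / (0.40 + 0.5 × 0.60) = 57.1%

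*Day against night (f = 1, s = 0.8 in both):* 90% wear by day gives 0.9 × 0.8 = 72%; 70% by night gives 0.7 × 0.8 = 56%. Detection is identical, yet the figures differ by 16 points.

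**The case against.** The strongest reply is that this is a choice of what to estimate. The objective speaks of everyday activities, and an alarm that is often off does miss episodes in everyday use. All-episode sensitivity is a legitimate measure. That stands, but the plan does not say which measure it means, and it calls the objective technical performance with wear as a separate endpoint.

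Second, some context is already planned: connected hours by day and night, and sensitivity on induced episodes alone. This helps, but average hours do not show whether the unit was on at a given episode.

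Third, the distortion may be small. Table 2 does not score every no-alarm episode as missed; in the half-scored case, 90% wear costs about 5 points rather than 8. Subjects have impaired awareness, and alarms prompt glucose measurement, so off-device episodes may be under-recorded and their share smaller than the share of time off. If there were 30 to 60 scored episodes (an assumption), a simple 95% half-width around 80% is 1.96 × √(0.8 × 0.2 / n), or about 14 to 10 points before clustering. A shift of 5 to 8 points lies inside that. This limits the consequence at high wear. It does not help at low wear, nor make a one-directional shift harmless when the figure guides algorithm work.

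Fourth, the log book itself is not in the documents, and the list of its contents need not be complete. Wear at onset may already be recorded. Even so, no stated analysis rule uses it.

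Finally, a not-worn category could let real misses be relabelled, since the sponsor classifies the alarms. That risk is real and shapes the fix.

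**Conclusion.** The concern holds. Applied as written, the rules make primary sensitivity depend on both wear and detection, and nothing in the plan separates them. Its size cannot be stated, because no H02 wear figure is given. In the illustrations, 80% detection while worn reads 72% at 90% wear and 40% at 50% wear under section 2.2. With half of no-alarm episodes scored as missed under Table 2, 88.9% falls to 83.7% and 57.1%. These rest on assumed values and on wear being independent of detectability.

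The study is descriptive, with about 12 completers and no success threshold, so no formal decision turns on this. It should still be corrected, because a primary endpoint has two readings and the remedy is cheap. Confidence is medium, as actual wear and the full log-book content are unknown.

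**What to change.** 1. Add a device-not-worn category to Table 2.
2. In sections 2.2 and 7.5.1, define technical-performance sensitivity on validated episodes starting while the day or night unit was worn in alarm-on mode.
3. Beside it, report all-episode (in-use) sensitivity and the number of off-device episodes, each by day and night. Showing all three exposes any relabelling of misses as not worn.
4. Take wear at onset from a log-book item asking whether the device was on, if none exists already. Cross-check it against connection times if these are time-stamped, which the plan does not state. Set wear status before the episode is classified.
5. Do not use connection status alone. An unworn unit and a failed link on a worn unit both show as not connected, and link failures on a worn unit should remain false negatives.

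The cost is wording in two sections and Table 2, possibly one log-book item, and a small tabulation. Neither measure is given up. The drawbacks are fewer episodes in the on-device denominator, and recall error because subjects with impaired awareness would report wear around a hypoglycaemic episode.

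### Section 2.2 divides the primary (spontaneous) PPV and the insulin-induced PPV by all device alerts, although section 7.5.1 bases each on its own kind of episode

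*Combined protocol and SAP*

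**What the plan says.** Section 2.2 sets out three PPVs. The primary one relates validated "spontaneous hypoglycaemic episodes detected by the hyposafe H02 compared to the total number of alerts from the hyposafe H02 after 12 weeks" of monitoring, visits 5 to 10. The overall PPV has the same denominator and window, with spontaneous and induced episodes together in the numerator. The third is "Proportion of insulin-induced hypoglycaemic episodes detected by the hyposafe H02 compared to the total number of alerts from the hyposafe H02", and it has no visit window. None of the three denominators is restricted by the circumstances in which an alert arose. The two footnotes say how an episode is validated. They do not say which alerts are counted.

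Section 7.5.1 describes the data for each figure differently. The primary sensitivity and PPV are "based on spontaneous hypoglycaemic episodes". For the secondary figures, "data from the insulin-induced hypoglycaemia will be added to calculate the overall" sensitivity and PPV, and the data for these are described as "spontaneous and insulin-induced hypoglycaemia episodes) after 12 weeks of monitoring (from visit 5 to visit 10". A separate line states: "The sensitivity and positive predictive value will also be calculated based data from the insulin-induced hypoglycaemic episodes only".

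Sections 3.1 and 7.5.1 give each subject two provoked sessions. Sections 3.1, 4.1 and 7.1 aim for at least 12 completers.

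**The concern.** An alert in a provoked session cannot enter the primary numerator, because the episode is not spontaneous. Nothing in section 2.2 takes that alert out of the primary denominator. Section 7.5.1 places the induced data within visits 5 to 10, so the alert is counted there with the same effect as a false alarm. The better the device detects provoked hypoglycaemia, the lower its primary PPV becomes. In the other direction, every everyday alert, true or false, lowers the induced PPV.

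PPV is one of the two primary performance endpoints. Section 7 plans no comparative analysis, so the reported estimate is itself the result. Section 1.2 says the study is to verify that the device works as intended before a larger study, and section 8.10 says the report will serve further development and approval. A headline figure that depends on which section the analyst follows serves neither purpose well.

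**Working it through.** The plan states no PPV target, expected PPV or alert count, so there is no figure to reproduce. The check applies the two rules to the same data.

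**Inputs from the documents.** Two sessions per subject and 12 completers give 12 × 2 = 24 sessions.

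**Assumptions.** There are T true and F false everyday alerts in visits 5 to 10. There are S session alerts, all correct and all in that window. Each detected episode gives one alert, so episodes and alerts can be counted in the same units. S = 24 means that every session alerts within the window. S = 12 means that half of them do.

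**Formulas.** Let s = S/(T + F + S), the share of alerts that arise in sessions.

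- Primary PPV on everyday alerts only: T/(T + F)
- Primary PPV under section 2.2 as written: T/(T + F + S) = [T/(T + F)] × (1 − s)
- Induced PPV under section 2.2 as written: S/(T + F + S) = s, its maximum even when every session alert is correct
- Overall PPV: (T + S)/(T + F + S)

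**Results for the primary PPV.**

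| Assumed T / F | S | Everyday alerts only | Section 2.2 as written |
|---|---|---|---|
| 30 / 30 | 12 | 30/60 = 50.0% | 30/72 = 41.7% |
| 30 / 30 | 24 | 30/60 = 50.0% | 30/84 = 35.7% |
| 120 / 240 | 12 | 120/360 = 33.3% | 120/372 = 32.3% |
| 120 / 240 | 24 | 120/360 = 33.3% | 120/384 = 31.3% |

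**Results for the induced PPV.** With S = 24, all correct, section 2.2 gives 24/84 = 28.6% in the first setting and 24/384 = 6.3% in the second. On session alerts alone it is 24/24 = 100%.

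**Check on the overall PPV.** With T/F = 30/30 and S = 24 it is 54/84 = 64.3%, which is the right value for all episodes over all alerts. It also equals 35.7% + 28.6%. With one shared denominator, the primary and induced figures are only the two parts of the overall PPV, and neither is a predictive value for its own setting.

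**High alert rate.** Visits 5 to 10 cover 12 weeks, or 84 days, so 12 completers contribute 12 × 84 = 1,008 subject-days. At an assumed one everyday alert per subject-day, s = 24/1,032 = 2.3%, and an everyday PPV of 50% becomes 50% × (1 − 0.023) = 48.8%. The induced PPV could then not exceed 2.3%.

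**The case against.** The strongest reply is that section 7.5.1 already settles the matter. It ties the primary PPV to spontaneous episodes, brings in induced data only for the overall figure, and computes the induced figure from induced episodes alone. A sensible analyst would not divide session detections by 12 weeks of everyday alerts, and the missing visit window on the induced PPV fits a session-only denominator. As an account of intent this is probably right. But section 7.5.1 speaks of episodes and never restates a denominator, while the endpoint definition does state one, and it is different. Neither section says when a session begins and ends for the purpose of allocating alerts.

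A second reply is that the size is assumed. That stands. At high alert rates the primary PPV barely moves, and if no session fell within visits 5 to 10 it would not move at all. The flow chart in Table 1, as extracted, puts the second induced-hypoglycaemia mark under visit 11, outside the window. The same extraction puts the EEG quality test under visits 5 and 11, where section 7.5.1 says visits 4 and 10, so its columns cannot settle the timing. Section 7.5.1 does place the combined data within visits 5 to 10.

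A third reply is that nothing hangs on the number. There is indeed no PPV target, test or go/no-go rule, so the harm is confined to the reported estimate.

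**Conclusion.** The point holds for two of the three PPVs. As written in section 2.2, the primary PPV equals the everyday PPV multiplied by (1 − s), and the induced PPV cannot exceed s. The direction needs no assumed counts, provided that at least one session alert falls within visits 5 to 10 (for the primary) and that there are everyday alerts (for the induced). The size does depend on assumed counts. The primary PPV loses up to about 14 percentage points in the sparse setting (50% to 35.7%) and 1 to 2 points in the denser one. The induced PPV is badly distorted in both. Section 7.5.1 itself expects that spontaneous episodes may be few. If everyday alerts are few as well, the effect on the primary is largest.

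Two stronger readings are tempting, and the documents do not support them.

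- A reader might infer that all three PPVs are wrong because they share a denominator. The overall PPV is not: all validated episodes over all alerts in visits 5 to 10 is a correct pairing and agrees with section 7.5.1.
- A reader might infer that Table 2 contradicts section 2.2, because alarms are used "to classify a hypoglycaemic alarm according to categorisation displayed in Table 2" and an alarm with neither a glucose value nor symptoms is left uncategorised there. That would require a PPV computed as true positives over true plus false positives, and no section gives that formula. Section 2.2 already counts every alert, so such alarms stay in the denominator.

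**What to change.** In section 2.2, and repeated in section 7.5.1:

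- **Primary PPV:** limit numerator and denominator to alerts in visits 5 to 10 outside the provoked sessions.
- **Induced PPV:** limit both to alerts during the sessions.
- **Session window:** define it before the data are read. First to last plasma glucose sample is one option.
- **Overall PPV:** leave it as defined.

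The same limits should carry through to the split by time of day, since section 7.5.1 states: "Sensitivity and positive predictive value will be calculated for daytime and night-time, separately".

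As a reporting suggestion only, confirm that alarms left uncategorised by Table 2 remain in the denominator, and report how many there are. Section 7.5.3 instructs a glucose measurement at each alarm, which should keep them few, but it also makes following that instruction an endpoint, so some are to be expected.

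The cost is a change of wording in two sections. Session start and end times must be available to the analysis. The documents do not confirm that these reach the database, so they may need to be added to the data collected.
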